### 7.2 Secondary Outcomes

- Sensitivity, Specificity, PPV, NPV of each tracer method
- Deep learning model performance metrics (AUC, accuracy, F1 score, Brier score)
- Number of sentinel lymph nodes identified per participant
- Total number of lymph nodes retrieved
- Feature importance rankings from SHAP analysis

### 7.3 Safety Outcomes

- Surgical complications (hypoparathyroidism, recurrent laryngeal nerve injury, bleeding, infection)
- Tracer-related adverse events (allergic reactions, injection site reactions)
- Time Frame: Within 30 days after surgery

## 8. DATA COLLECTION AND MANAGEMENT

### 8.1 Clinical Data Collection

A total of 32 clinical variables will be collected for each participant:

Demographics (3 variables): Age, sex, body mass index (BMI)

Ultrasound features (9 variables): Tumor size, tumor margin, calcification pattern, aspect ratio, internal echoes, homogeneity, intratumoral blood flow, peritumoral blood flow, TI-RADS classification

Pathological features (10 variables): Tumor location, laterality, multifocality, capsular invasion, extrathyroidal extension (ETE), Hashimoto's thyroiditis, T stage, SLN location, SLN metastasis status, number of positive SLNs

Genetic data: BRAF mutation status and other relevant mutations

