## **2.4 Role of Deep Learning**

Deep learning (DL) is well suited to extract high-dimensional spatiotemporal patterns from surgical videos and to integrate them with clinicopathological variables, potentially revealing predictive signals beyond what is apparent to the human eye. By applying explainable artificial intelligence (XAI) methods such as SHAP (SHapley Additive exPlanations), we can identify influential features and provide interpretable outputs to support intraoperative decision-making.

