## 3. STUDY OBJECTIVES AND HYPOTHESES

### 3.1 Primary Objectives

1. To compare the sentinel lymph node detection rate among three tracer methods: ICG alone, CNs alone, and ICG+CNs dual-tracer combination.
2. To evaluate and compare the diagnostic performance (sensitivity, specificity, PPV, NPV) of each tracer method for predicting central lymph node metastasis.
3. To develop and validate deep learning models using multimodal features (spatiotemporal video features + clinical variables) for predicting second-echelon lymph node metastasis (SeLNM) and non-sentinel lymph node metastasis (NsLNM).

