### 3.3 Hypotheses

Primary Hypothesis: The ICG+CNs dual-tracer combination will demonstrate superior sentinel lymph node detection rate compared to either tracer alone.

Secondary Hypothesis: Time-series fluorescence-flow signatures, combined with spatial structural cues and clinicopathological factors, will improve prediction of SeLNM and NsLNM compared with SLN status alone.

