#### 7.1.2 Sentinel Lymph Node Metastasis (SLNM) Status

Definition: Presence or absence of cancer metastasis in the sentinel lymph node.

Classification: Positive (macrometastasis or micrometastasis) or Negative

Gold Standard: Final histopathological examination (paraffin section)

Time Frame: Within 7 days after surgery

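### The model inputs include tumour pathology with no intraoperative source, and sentinel-node results of unstated source, so performance may not transfer to the claimed use in theatre

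*Combined protocol and SAP*

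**What the plan says.** Objective 3 in section 3.1 is to develop and validate models "using multimodal features (spatiotemporal video features + clinical variables") for second-echelon (SeLNM) and non-sentinel (NsLNM) metastasis. The secondary hypothesis in section 3.3 is that fluorescence time-series signatures, "combined with spatial structural cues and clinicopathological factors, will improve prediction of SeLNM and NsLNM compared with SLN status alone".

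The clinical variables are defined only in section 8.1: "A total of 32 clinical variables will be collected for each participant". Ultrasound features form one group. A separate group begins "Pathological features (10 variables): Tumor location, laterality, multifocality, capsular invasion, extrathyroidal extension (ETE), Hashimoto's thyroiditis" and continues "T stage, SLN location, SLN metastasis status, number of positive SLNs". No time point or source is attached to any item. Section 9.4 covers architectures, training and validation but names no predictors.

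On pathology, section 7.1.2 gives, for SLN metastasis status, "Gold Standard: Final histopathological examination (paraffin section"), with a time frame of 7 days after surgery. SeLNM and NsLNM carry the same time frame in sections 7.1.3 and 7.1.4. Section 6.5 bases the final diagnosis on paraffin and confines frozen section to lymph nodes.

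On intended use, section 2.4 says the explainable models will "provide interpretable outputs to support intraoperative decision-making". Section 3.2 makes the clinical utility of intraoperative AI support a secondary objective, and section 9.6 plans decision curve analysis.

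**The concern.** A model meant for use during surgery should be assessed on what is known during surgery. If some of its inputs arrive with the paraffin report, the estimate answers a different question: how well nodal status can be predicted once the rest of the pathology is in hand.

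Three results are exposed:

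- **Performance and decision curves** would describe a predictor set that is not fully available in theatre.
- **SHAP rankings** could be led by variables the surgeon does not yet have.
- **The comparison with SLN status alone** could favour the full model because of postoperative T stage or extrathyroidal extension, when the hypothesis is about the video signal.

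**Working it through.** No sample size, power or alpha figure is involved, so there is no stated result to reproduce. The check is on which inputs are defined and when the plan makes each one available.

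**1. What the inputs are.** Section 3.1 says clinical variables and section 3.3 says clinicopathological factors. Section 8.3 defines only the video features. Section 8.1 is therefore the only definition of the non-video inputs, and nothing selects a subset of it. The list is also incomplete: its counted groups give 3 + 9 + 10 = 22 of the 32 stated, leaving 32 − 22 = 10. The only remaining entry is an uncounted genetic one that names BRAF and otherwise refers to unspecified mutations.

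**2. When the ten pathological items become known, on the plan's own procedures:**

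- Known before or during surgery: tumour location, laterality, SLN location (3).
- Obtainable from frozen section, but with paraffin as the plan's reference: SLN metastasis status, number of positive SLNs (2).
- No intraoperative pathology source stated: T stage, extrathyroidal extension, capsular invasion, multifocality, Hashimoto's thyroiditis (5).

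The total is 3 + 2 + 5 = 10. The last group rests on three facts. Section 8.1 lists these items apart from the ultrasound features. The preoperative tissue in section 6.1 is fine-needle aspiration for cytological confirmation. Frozen section in sections 6.3 and 6.5 is of lymph nodes, not the primary tumour. The only tissue source left is the postoperative paraffin work-up.

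**3. Whether validation would show the problem.** It would not. In the 10-fold cross-validation of section 9.4.3, each held-out tenth carries the same inputs as the training data. No analysis restricted to intraoperative inputs is planned.

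**4. Why the source of SLN status matters (illustration for one predictor only).** For a binary predictor, AUC = (sensitivity + specificity)/2. Assume that frozen section detects a fraction f of paraffin-positive SLNs, gives no false positives, and misses nodes independently of the target. Sensitivity s becomes s·f and specificity p becomes 1 − (1 − p)·f, so AUC = 0.5 + f·(s + p − 1)/2. The documents give no f; take 0.70 to 0.95. Borrow s and p from section 5.4, where they are tracer planning values and not values for SeLNM or NsLNM:

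- s = 0.85, p = 0.90: 0.875 with paraffin; 0.5 + 0.95 × 0.375 = 0.856 at f = 0.95; 0.5 + 0.70 × 0.375 = 0.7625 at f = 0.70.
- s = 0.50, p = 0.90: 0.700 with paraffin; 0.5 + 0.95 × 0.200 = 0.690 at f = 0.95; 0.5 + 0.70 × 0.200 = 0.640 at f = 0.70.

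Under these assumptions, paraffin values overstate the intraoperative AUC of SLN status alone by about 0.01 (0.700 − 0.690) to 0.11 (0.875 − 0.7625). This shows a direction and a reason to give the model and the comparator the same SLN reading. It does not size the effect on the full model.

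**The case against.** The best defence is that section 8.1 lists what is collected, across all three groups, and is not headed as a predictor list. The plan never says that final-pathology values enter the model. Its pathological heading is loose, since it also holds tumour location, laterality and SLN location. The paraffin reference in section 7.1.2 defines an outcome, and the frozen section in section 6.3 could supply the two SLN variables. Sections 6.3 and 10.4 state that the deep learning analysis is retrospective and does not affect surgery. If model and comparator share one SLN value, its source affects both.

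Much of this stands, and it rules out stronger readings that a reader might infer:

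- That all ten items are postoperative. Three are known by surgery, and two have a frozen-section route.
- That the reported performance will not apply in theatre. The documents show only that it may be optimistic.
- That the outcome itself leaks into the predictors. None of the ten items is SeLNM or NsLNM status.
- That patients in this study are exposed to the predictions. They are not.

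What does not stand is the conclusion that nothing needs changing. No other section defines the inputs, so following the plan as written leads to the list in section 8.1. Frozen section of nodes does not cover the five primary-tumour items. Retrospective computation protects these patients but does not make the estimate valid for the intraoperative use claimed in sections 2.4 and 3.2. A shared SLN value would not remove a gain produced by postoperative T stage or extrathyroidal extension.

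**Conclusion.** The point holds in a limited form. Five of the ten pathological variables have no intraoperative pathology source in the plan, and the source of two more is unstated. Performance, decision curves and SHAP rankings may therefore be optimistic for use in theatre, and a gain over SLN status alone could not be credited to the video features with confidence.

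This rests on reading section 8.1 as the model's clinical inputs, which sections 3.1 and 3.3 make the natural reading but do not state outright. It also assumes that the five tumour variables are taken from tissue and not from imaging or gross inspection. If the sponsor can show that imaging, gross or frozen-section values are used throughout, what remains is a gap in specification.

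The size of the effect on the full model cannot be computed. It would need the frozen-section detection rate and the strength of each variable's association with SeLNM and NsLNM, and the documents give neither.

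**What to change.** In sections 8.1 and 9.4:

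- State the source (ultrasound, gross, frozen, paraffin, genetic) and the time point of each input, and complete the list of 32.
- Make the primary model the one restricted to inputs known before the end of the operation: demographics; ultrasound features; tumour location and laterality; SLN location; genetic results already returned; video features; and frozen-section SLN status and count. For the five tumour variables, use preoperative imaging or gross intraoperative values where recorded, and otherwise omit the variable.
- Use the same frozen-section SLN status for the SLN-alone comparator in the section 3.3 hypothesis.
- Report the model with paraffin-based variables only as a sensitivity analysis, labelled postoperative.

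The cost is mainly SAP wording and refitting on data largely in hand. The reported AUC may be lower. One point needs checking first: frozen section is performed, but section 8.1 has no separate field for its result, so the sponsor must confirm that it is recorded apart from the paraffin reading.

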### 8.2 Video Data Processing

For the ICG+CNs group:

- Extract 3-minute segment showing complete SLN visualization process
- Resample to 150 frames (5 fps) at 1920×1080 resolution
- Manual ROI annotation by two senior surgeons (>10 years experience)
- Generate binary mask images for each frame
- Resize to standard 512×512 dimensions

### 8.3 Feature Extraction

Spatial Features (2,048 dimensions):

- Deep image features from EfficientNet-B5 pre-trained model
- Grayscale characteristics
- Shape and morphological features
- Hu moment descriptors

Temporal Features (20 dimensions):

- Frame-to-frame difference features (4 dimensions)
- Optical flow features (3 dimensions)
- Fluorescence time-series features (20 dimensions)

Dimensionality Reduction: Principal Component Analysis (PCA) to 32 dimensions

### 8.4 Data Quality Assurance

- Double data entry for clinical variables
- Range checks and logical validation
- Regular data audits
- Secure electronic data storage with backup
- De-identification of all data before analysis

## 9. STATISTICAL ANALYSIS PLAN

### 9.1 Analysis Populations

Intention-to-Treat (ITT) Population: All enrolled participants who received the assigned tracer injection.

Per-Protocol (PP) Population: All participants who completed the study according to the protocol without major deviations.

Safety Population: All participants who received any study intervention.

### 9.2 Descriptive Statistics

- Continuous variables: Mean  $\pm$  standard deviation (normal distribution) or median with interquartile range (non-normal distribution)
- Categorical variables: Frequencies and percentages
- Normality testing: Shapiro-Wilk test
- Baseline characteristics compared among three groups

### 9.3 Primary Outcome Analysis

#### 9.3.1 SLN Detection Rate Comparison

- Chi-square test or Fisher's exact test for comparison among groups
- 95% confidence intervals for detection rates
- Pairwise comparisons with Bonferroni correction

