## 1. PROTOCOL SUMMARY

Study Title	Deep Learning-Based Intraoperative Dual-Tracer Video Analysis of Sentinel Lymph Node Mapping for Metastasis Prediction in cN0 Papillary Thyroid Carcinoma
Study Type	Prospective Observational Cohort Study
Registry Number	NCT06871956
Study Population	Adults ( $\geq 18$ years) with clinically node-negative papillary thyroid carcinoma (cN0-PTC)
Sample Size	336 participants (112 per group $\times$ 3 groups)
Study Groups	1) ICG Group, 2) CNs Group, 3) ICG+CNs (Dual-Tracer) Group
Primary Outcomes	SLN detection rate, SLNM status, SeLNM, NsLNM
Study Duration	April 2024 - October 2024 (enrollment); 12 months follow-up
Study Sites	The First Affiliated Hospital of Chongqing Medical University, Chongqing, China
Principal Investigator	[name], MD, PhD

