## 4. STUDY DESIGN

### 4.1 Study Type and Design

This is a prospective, single-center, three-arm observational cohort study. Participants will be allocated to one of three groups based on the sentinel lymph node mapping technique used during their thyroid surgery.

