### 5.2 Inclusion Criteria

1. Age  $\geq$ 18 years at the time of enrollment
2. Histologically confirmed papillary thyroid carcinoma by preoperative fine-needle aspiration biopsy
3. Clinically node-negative (cN0) status confirmed by preoperative imaging (ultrasound and/or cross-sectional imaging showing no evidence of lymph node metastasis)
4. Scheduled to undergo thyroid surgery with simultaneous central lymph node dissection
5. Willing and able to provide written informed consent
6. Complete preoperative clinical data available

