### 5.3 Exclusion Criteria

1. History of previous neck surgery
2. History of external beam radiotherapy to the head and neck region
3. Diagnosis of thyroid malignancy other than papillary thyroid carcinoma
4. Known allergy or hypersensitivity to indocyanine green (ICG), iodine, or carbon nanoparticles
5. Severe hepatic insufficiency (ICG is metabolized by the liver)
6. Pregnancy or breastfeeding
7. Incomplete medical records or missing essential preoperative data
8. Refusal to undergo dual-tracer imaging procedure
9. Participation in another interventional clinical trial that may interfere with the current study

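### The claim that the dual tracer has a superior SLN detection rate rests only on crude tests, in an observational cohort whose tracer-selection rule is not stated

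*Combined protocol and SAP*

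**What the plan says.** Section 3.3 states the primary hypothesis: "The ICG+CNs dual-tracer combination will demonstrate superior sentinel lymph node detection rate compared to either tracer alone". The Protocol Summary gives the study type as "Prospective Observational Cohort Study". Section 4.1 says: "Participants will be allocated to one of three groups based on the sentinel lymph node mapping technique used during their thyroid surgery". Section 4.2 sets three groups of 112. Section 9.1 defines the intention-to-treat population by an assigned tracer, but no section describes randomisation, alternation, a calendar rule, or surgeon or patient choice.

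For the detection rate, section 9.3.1 plans "Chi-square test or Fisher's exact test for comparison among groups", 95% confidence intervals for the rates, and Bonferroni-corrected pairwise comparisons. Section 9.2 compares baseline characteristics across the groups but attaches no action to the result. The sensitivity analyses in section 9.8 concern missing data. The DeLong and Wald procedures in section 9.6 compare prediction models, not tracers.

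Eligibility is common to all groups. Everyone must be "Scheduled to undergo thyroid surgery with simultaneous central lymph node dissection", and the exclusions include "Known allergy or hypersensitivity to indocyanine green (ICG), iodine, or carbon nanoparticles" and "Refusal to undergo dual-tracer imaging procedure".

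**The concern.** A superiority claim between groups that were not randomised needs some control for the reasons why patients received different tracers. Section 9.3.1 has none. Bonferroni limits false claims from multiple testing and does nothing about confounding.

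Detection depends on ultrasound-guided injection at several points and on recognising the node by stain or fluorescence (sections 6.2.1 to 6.2.3), so operator, calendar period and tumour features could plausibly affect it. If any of these differ by group, the planned test cannot separate them from the tracer. The error could run either way: a false claim for the dual tracer, or a real benefit hidden. If section 9.2 did show an imbalance, the analyst would have to choose a response after seeing the data.

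**Working it through.** **Reading the sections together.** The hypothesis (3.3) is comparative, the design (1, 4.1) is observational, the test (9.3.1) is crude, the baseline comparison (9.2) has no consequence, and the sensitivity analyses (9.8) address a different problem. This establishes the omission without arithmetic. The plan has no figure to reproduce here: the sample size in section 5.4 is built on sensitivity (85% against 50%), not on detection rate.

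**Illustration of size.** From the documents: 112 per group and two-sided alpha 0.05. Bonferroni over three pairs gives 0.05/3 = 0.0167. Assumed, with no support in the documents: the detection rates, the effect of one binary prognostic factor, its share in each group, and that both single-tracer groups are alike. There is no true tracer effect.

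Crude rate = (1 − share) × rate without the factor + share × rate with it.

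- A: factor lowers detection from 95% to 75%; share 30% dual, 60% single. Dual 0.70 × 0.95 + 0.30 × 0.75 = 0.89; single 0.40 × 0.95 + 0.60 × 0.75 = 0.83.
- B: 95% to 80%; 30% against 50%. Dual 0.70 × 0.95 + 0.30 × 0.80 = 0.905; single 0.50 × 0.95 + 0.50 × 0.80 = 0.875.
- C: 95% to 75%; 30% against 40%. Dual 0.89; single 0.60 × 0.95 + 0.40 × 0.75 = 0.87.

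Let c(x) be the probability, given x detections in the dual group, that the Pearson test against one single-tracer group is significant in favour of the dual tracer. With P(x) binomial, one pair = Σ P(x)c(x), both pairs = Σ P(x)c(x)², and at least one = Σ P(x)[1 − (1 − c(x))²]. Exact enumeration of a false finding for the dual tracer gives:

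| Case | One pair | Both | At least one |
|---|---|---|---|
| A | 13.1% | 5.1% | 21.2% |
| B | 4.5% | 1.2% | 7.9% |
| C | 2.6% | 0.6% | 4.6% |
| No imbalance (0.87 in all groups) | 0.8% | 0.13% | 1.5% |

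Fisher's test gives lower figures (A: 3.4% for both).

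**The opposite direction.** Assume single-tracer rates of 85% without the factor and 65% with it, the factor in 30% of single-tracer patients (0.70 × 0.85 + 0.30 × 0.65 = 0.79), and a true gain of 10 points. Power by share of the factor in the dual group:

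| Share in dual group | Dual rate | One pair | Both |
|---|---|---|---|
| 30% (balanced) | 0.89 | 36% | 21% |
| 40% | 0.87 | 21% | 9% |
| 60% | 0.83 | 5% | 1% |

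**Would section 9.2 reveal it?** If the factor is recorded, a pairwise baseline test at 0.05 flags 30% against 60% in 99.6% of studies, but 30% against 40% in only 35%.

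**The case against.** The strongest reply is that the harm is hypothetical. Every rate, factor effect and imbalance above is assumed, and the documents link no recorded variable to detection failure or to tracer choice. That stands: the omission is certain and the bias is not.

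A reader might infer that the plan would produce a false superiority claim 13% or 21% of the time. The documents do not support that. The hypothesis is most naturally read as beating both single tracers, so the relevant figures are 0.6% to 5.1%. The top of that range needs a factor costing 20 points of detection at 30% against 60%, which section 9.2 would almost always show if the factor is recorded. The masking figures also partly reflect low power, since power to beat both is only 21% under perfect balance.

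A reader might also infer that the groups are known to be confounded. They are not. Equal groups of 112 and the wording about allocation and assignment fit a protocol-driven scheme. If that scheme was random, saying so settles the adjustment question. Common eligibility also reduces tracer choice driven by contraindication or refusal, though not completely: only severe hepatic insufficiency and known allergy are excluded.

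Finally, adjustment may miss what matters most. Section 8.1 names neither operator nor surgery date, and the documents do not show that the variables it does name affect detection. That limits what the fix can achieve, but does not justify having no adjustment.

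**Conclusion.** The point holds and should be fixed before detection rates are analysed. The plan makes a superiority claim in an observational cohort, does not say how the tracer is chosen, and includes no control for confounding in the comparison that tests the claim. Whether bias exists, and in which direction, cannot be derived from the documents.

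Under the assumed inputs, false superiority over both single tracers is small for a modest imbalance and reaches about 5% only for a large imbalance on a strong factor. A modest imbalance against the dual tracer can still cost power. These figures indicate scale and are not estimates for this study. The conclusion does not depend on them, but it does depend on allocation not having been random.

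**What to change.** 1. State in section 4.1 how the tracer is chosen for each participant, and reconcile grouping by the technique used with the assigned tracer in section 9.1.
2. Unless allocation was random, add to section 9.3.1 one pre-specified covariate-adjusted analysis as the basis for the comparative conclusion: a logistic model standardised to all analysed participants, with a penalised (Firth) fit if detection failures are few. Set the threshold for few in advance. Report adjusted pairwise risk differences with 95% confidence intervals and keep Bonferroni.
3. Use a short list known before injection: age, sex, BMI, ultrasound tumour size, TI-RADS, and tumour location and laterality. Section 8.1 files the last two under "Pathological features (10 variables): Tumor location, laterality, multifocality", but the ultrasound-guided injection around the tumour means they are known beforehand, so take them from the preoperative ultrasound. Exclude SLN location, SLN metastasis status and number of positive SLNs, which follow the tracer.
4. Add operator and surgery date if they can be retrieved and overlap across groups. If tracers were used in consecutive blocks, state that period cannot be adjusted for.
5. Report the crude test alongside, and word conclusions as associations.

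The cost is SAP text, a sentence on selection and retrieval of two items. Precision falls slightly: in case A the standard error of a pairwise difference rises from 4.6 points, √(0.89 × 0.11/112 + 0.83 × 0.17/112), to about 5.0 in simulation. With about 12 failures among 336, an unpenalised model gave simulated pairwise error of 2.5% to 2.7% against a nominal 1.7% (2.1% with about 34 failures), which is the reason for the penalised option. The penalised fit itself was not simulated. Unmeasured confounding remains.
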